**ARM 2 STUDY PROCEDURES**

**VISIT 2 (14 ± 2 days following Visit 1)**

**Subjects must present with study lenses on eye for at least 2 hours.**

| ARM 2  |   |   |     |
|---|---|---|-----|
| Visit 2: Treatment 1, 2-Week Follow-Up; Treatment 2 Fitting |   |   |     |
| Step  | Procedure   | Details   |     |
| 2.1.  | Adverse Events and Concomitant Medications Review | Review any changes to the subject's medical history or concomitant medications from the previous study visit. Record any changes, and any adverse events. | N/A |
| 2.2.  | Wear Time   | Record the average wear time and comfortable wear time.   | N/A |
| 2.3.  | Compliance  | Confirm compliance with the prescribed wear schedule.   | N/A |
| 2.4.  | Subject Reported Ocular Symptoms                  | Subjects will respond to a verbal open-ended symptoms questionnaire.  |     |

**Clinical Study Protocol**  
**Johnson & Johnson Vision Care, Inc.**

| ARM 2  |                                |  |
|---|--------------------------------|--|
| Visit 2: Treatment 1, 2-Week Follow-Up; Treatment 2 Fitting |                                |  |
| Step  | Procedure                      | Details  |
| 2.5.  | CLDEQ-8 Questionnaire          | 
The subject will respond to the CLDEQ-8 Questionnaire (Appendix A).
 
NOTE: If subjects no longer meet score criteria of <math>\geq 15</math>, the lenses will be removed by the subject and discarded. The subject will be discontinued and proceed to final evaluation (F.1)
   |
| 2.6.  | Follow Up questionnaires       | 
The subject will respond to the CLUE and MRD Follow Up Questionnaire (Appendix A)
   |
| 2.7.  | Entrance Visual Acuity         | 
Record the distance Snellen visual acuity with the contact lenses (OD, OS) to the nearest letter. Subjects must read the smallest line until at least 50% of the letters are read incorrectly.
  |
| 2.8.  | Subjective Lens Fit Assessment | 
Evaluate overall lens fit acceptance (acceptable or unacceptable) based on centration, movement and other fitting characteristics.
 
An unacceptable fit is deemed by one of the following criteria:
 
 
• limbal exposure at primary gaze or with extreme eye movement.
 
• edge lift.
 
• excessive movement in primary and up gaze.
 
• insufficient movement in all three of the following conditions: primary gaze, up gaze, and Josephson push up.
 
 
NOTE: if lens fit is unacceptable subject will be discontinued from the study.
 |
| 2.9.  | Lens Removal and Discard       | 
The lenses will be removed by the subject and discarded.
  |

**Clinical Study Protocol**  
**Johnson & Johnson Vision Care, Inc.**

| ARM 2  |                                |  |
|---|--------------------------------|--|
| Visit 2: Treatment 1, 2-Week Follow-Up; Treatment 2 Fitting |                                |  |
| Step  | Procedure                      | Details  |
| 2.10.   | Slit Lamp
Biomicroscopy     | 
FDA Slit Lamp Classification Scale will be used to grade the findings and determine eligibility.
 
If the subject has a Grade 3 or higher slit lamp finding, it will be recorded as an Adverse Event and followed per protocol. If discontinued a final examination must be completed.
 
If the clearance of the fluorescein needs to be expedited, preservative-free rewetting drops or saline may be instilled.
   |
| 2.11.   | Lens Selection                 | Assign study lens 2 per the randomization, based on subjective best sphere refraction.   |
| 2.12.   | Lens Insertion                 | The subject inserts the study lenses. Record the time of lens insertion.
Check for lens damage under the slit lamp before proceeding with lens settling.
Replace damaged lenses if applicable.   |
| 2.13.   | Lens Settling                  | Allow the study lenses to settle for a minimum of 5 minutes.   |
| 2.14.   | Subjective Lens Fit Assessment | 
Evaluate overall lens fit acceptance (acceptable or unacceptable) based on centration, movement and other fitting characteristics.
 
An unacceptable fit is deemed by one of the following criteria:
 
 
• limbal exposure at primary gaze or with extreme eye movement.
 
• edge lift.
 
• excessive movement in primary and up gaze.
 
• insufficient movement in all three of the following conditions: primary gaze, up gaze, and Josephson push up.
 
 
NOTE: if lens fit is unacceptable subject will be discontinued from the study.
 |

**Clinical Study Protocol**  
**Johnson & Johnson Vision Care, Inc.**

| ARM 2  |   |  |
|---|---|--|
| Visit 2: Treatment 1, 2-Week Follow-Up; Treatment 2 Fitting |   |  |
| Step  | Procedure                               | Details  |
| 2.15.   | Subjective Best Sphere Over Refraction  | 
Perform a spherical over-refraction OD and OS using any acceptable means (ie, phoropter, trial lenses, flipper bars) in normal room illumination.
 
Confirm spherical endpoints with the duochrome (red-green) test: Neutrality is reached when the letters on both backgrounds appear equally clear/dark. If no neutrality point is obtained, the endpoint will be based on “first green”: first report of letters appearing clearer/darker on the green background.
 
If in the investigator’s clinical opinion, the subject is not responding well to duochrome, the subjective best sphere refraction endpoint will be recorded.
 
A plano over refraction must be achieved to continue.
 |
| 2.16.   | Lens Power Modification (if applicable) | 
Adjust the lens power if the subject’s best sphere over-refraction is not plano.
 
For each power modification, repeat steps (2.12-2.15).
 
Up to two power modifications are allowed.
   |
| 2.17.   | Subject Reported Ocular Symptoms        | Subjects will respond to a verbal open-ended symptoms questionnaire.   |
| 2.18.   | Exit Visual Acuity                      | Record the distance Snellen visual acuity (OD, OS) to the nearest letter. Subjects must read the smallest line until at least 50% of the letters are read incorrectly.   |
| 2.19.   | Continuance                             | 
For the subject to continue in the study, they must meet all three of the following criteria:
 
 
• Visual acuity is 20/25 or better OD and OS
 
• The lens fit is acceptable OD and OS
 
• Investigator approval
 
   |

**Clinical Study Protocol**  
**Johnson & Johnson Vision Care, Inc.**

| ARM 2  |             |  |
|---|-------------|--|
| Visit 2: Treatment 1, 2-Week Follow-Up; Treatment 2 Fitting |             |  |
| Step  | Procedure   | Details  |
|   |             | If the Investigator does not approve the dispensing of the study lens, then the study is terminated for that subject.  |
| 2.20.   | Dispense    | 
The lenses will be dispensed for a 12-16 day wearing period. During this time, they are required to wear the lenses at least 10 days and at least 8 hours per day that they are worn.
 
 
• Only study provided contact lenses and saline are permitted during the study.
 
• Dispense enough lenses to last the subject to their scheduled follow-up visit. *Do not dispense extras*.
 
• The lenses will be worn as daily wear/daily disposable only.
 
• Study provided non-preserved ophthalmic saline is permitted for rewetting if needed. Instruct the subject that since the saline is preservative-free, the product is to be disposed after single use due to potential exposure to microbial contamination from re-use of the product.
 
• Subjects will be scheduled for their 2-week follow up visit, ensuring that they wear the study lens at least two (2) hours on the day of the follow-up visit.
 
 
*NOTE: In the event a lens is lost or damaged, the subject will return to the clinical site for replacement. As much as reasonably possible, a damaged lens and packaging should be returned to the clinical site (wet, if possible) and then returned to the Sponsor. If lens damage is present, complete the Product Quality Complaint Form. The lens will be stored in labeled vial with saline, and clearly differentiated from the other worn lenses that will be shipped back to the Sponsor.
 |
| 2.21.   | Instruction | Advise the subject that at their next visit they will need to bring their spectacle or habitual contact lens in hand since the study will be complete.   |

**Clinical Study Protocol**  
**Johnson & Johnson Vision Care, Inc.**

**VISIT 3 (14 ± 2 days following Visit 3)**

**Subjects must present with study lenses on their eyes for at least 2 hours.**

| ARM 2                           |   |   |     |
|--|---|---|-----|
| Visit 3: Treatment 2, 2-Week Follow-Up |   |   |     |
| Step                                   | Procedure   | Details   |     |
| 3.1.                                   | Adverse Events and Concomitant Medications Review | Review any changes to the subject's medical history or concomitant medications from the previous study visit. Record any changes, and any adverse events.   | N/A |
| 3.2.                                   | Wear Time   | Record the average wear time and comfortable wear time.   | N/A |
| 3.3.                                   | Compliance  | Confirm compliance with the prescribed wear schedule.   | N/A |
| 3.4.                                   | Subject Reported Ocular Symptoms                  | Subjects will respond to a verbal open-ended symptoms questionnaire.  |     |
| 3.5.                                   | CLDEQ-8 Questionnaire                             | The subject will respond to the CLDEQ-8 Questionnaire (Appendix A)  |     |
| 3.6.                                   | Follow-up questionnaires                          | The subject will respond to the CLUE and MRD Baseline Questionnaire (Appendix A)  |     |
| 3.7.                                   | Preference  | The subject will respond to the Preference Questionnaire (Appendix A)   |     |
| 3.8.                                   | Entrance Visual Acuity                            | Record the distance Snellen visual acuity with the contact lenses (OD, OS) to the nearest letter. Subjects must read the smallest line until at least 50% of the letters are read incorrectly.  |     |
| 3.9.                                   | Subjective Lens Fit Assessment                    | 
Evaluate overall lens fit acceptance (acceptable or unacceptable) based on centration, movement and other fitting characteristics.
 
An unacceptable fit is deemed by one of the following criteria:
 
 
• limbal exposure at primary gaze or with extreme eye movement.
 
• edge lift.
 
• excessive movement in primary and up gaze.
 
• insufficient movement in all three of the following conditions: primary gaze, up gaze, and Josephson push up.
 
 |     |

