# Clinical Study Protocol

## Johnson & Johnson Vision Care, Inc.

|  |  |
|--|--|
|  | 

• I was satisfied with the quality of my vision at night (V014_1)

• I was very satisfied with the clarity of distant objects (V034_2)

• I was satisfied with the clarity of near objects (V035_1)

• I was very satisfied by the clarity of my vision at the end of the day (V037_2)

• My vision with these lenses was exceptional (V124_3)

 
4. MRD Questions:
 

• These lenses help to reduce the feeling of dryness at the end of the day (MIS01977)

• I would recommend them to people who experience dryness with their own contact lenses (P3_0021_p10)

• Have you been able to use these lenses for 8 hours or more with digital devices? (MIS01978)

 
Please think about your experience with your current contact lenses / the study contact lenses. Please indicate how you would rate the contact lenses on each of the following characteristics.
 

• Not making your eyes feel dry throughout the day (P3_0006_p38)

• Keeping your eyes from feeling dry at the end of the day (P3_0006_p39)

 
Please indicate how often, if ever, you experienced the following sensations when you wore your current contact lenses/ the study contact lenses.
 

• Burning (P3_0023_p01)

• Dryness (P3_0023_p02)

• Grittiness (P3_0023_p03)

 
5. Preference Questions:
 

• Thinking about the last two lenses you tried, which lens did you prefer overall? (PREF1)

• Overall Comfort (PREF10_3)

• Comfort at the end of the day (PREF10_5)

• Overall vision (PREF10_7)

• Keeping your eyes from feeling dry (PREF10_14)

 |
|--|--|

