# **Clinical Study Protocol**

## **Johnson & Johnson Vision Care, Inc.**

- I have experienced dry eyes (C041\_1)
  - The comfort of these lenses decreased throughout the day (C061\_1)
3. CLUE Vision Questions:
- I had very good vision at the end of the day (V004\_2)
  - I experienced fluctuations in the quality of my vision (V009\_1)
  - I was very satisfied with the quality of my vision in dim lighting (V013\_2)
  - I was satisfied with the quality of my vision at night (V014\_1)
  - I was very satisfied with the clarity of distant objects (V034\_2)
  - I was satisfied with the clarity of near objects (V035\_1)
  - I was very satisfied by the clarity of my vision at the end of the day (V037\_2)
  - My vision with these lenses was exceptional (V124\_3)
4. MRD Questions:
- These lenses help to reduce the feeling of dryness at the end of the day (MIS01977)
  - I would recommend them to people who experience dryness with their own contact lenses (P3\_0021\_p10)
  - Have you been able to use these lenses for 8 hours or more with digital devices? (MIS01978)
- Please think about your experience with your current contact lenses/ the study contact lenses. Please indicate how you would rate the contact lenses on each of the following characteristics.
- Not making your eyes feel dry throughout the day (P3\_0006\_p38)
  - Keeping your eyes from feeling dry at the end of the day (P3\_0006\_p39)
- Please indicate how often, if ever, you experienced the following sensations when you wore your current contact lenses/ the study contact lenses.
- Burning (P3\_0023\_p01)
  - Dryness (P3\_0023\_p02)
  - Grittiness (P3\_0023\_p03)
5. Preference Questions:
- Thinking about the last two lenses you tried, which lens did you prefer overall? (PREF1)
  - Overall Comfort (PREF10\_3)
  - Comfort at the end of the day (PREF10\_5)
  - Overall vision (PREF10\_7)
  - Keeping your eyes from feeling dry (PREF10\_14)

Other Endpoints:

Average Wear Time / Comfortable Wear Time

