### **2.3. Hypotheses**

Primary Hypothesis:

The Primary hypothesis will be evaluated between the two study arms; only the first period will be considered for the second study arm.

| Primary Hypotheses |   |
|--------------------|---|
| Endpoint           | Hypothesis  |
| CLUE Comfort       | The Test lens will be non-inferior to the Habitual lens with respect to the change in CLUE comfort score from baseline at 2-week follow-up. A non-inferiority margin of -5 points on the CLUE scale will be used. |

Secondary Hypotheses:

The primary hypothesis must be met in order to test the secondary hypotheses. The secondary hypothesis regarding the change in CLDEQ-8 Scores will be evaluated between the two study arms; only the first period will be considered for the second study arm. The remaining two secondary hypotheses will be evaluated within the second study arm only.

| Secondary Hypotheses          |  |
|-------------------------------|--|
| Endpoint                      | Hypothesis   |
| Change in CLDEQ-8 Total Score | The Test lens will be non-inferior to the Habitual lens with respect to the change in CLDEQ-8 total score from baseline at 2-week follow-up. A non-inferiority margin of 3 points on the CLDEQ-8 scale will be used. |
| CLDEQ-8 Total Score           | The Test lens will be non-inferior to the Habitual lens with respect to CLDEQ-8 total score at 2-week follow-up. A non-inferiority margin of 3 CLDEQ-8 points will be used.  |
| CLUE Comfort                  | The Test lens will be non-inferior to the Habitual lens with respect to CLUE comfort score at 2-week follow-up. A non-inferiority margin of -5 CLUE points will be used.   |

The primary hypothesis must be met in order to satisfy the objective of the study.

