**Clinical Study Protocol**  
**Johnson & Johnson Vision Care, Inc.**

| ARM 2 STUDY PROCEDURES     |  |   |  |   |
|--|--|---|--|---|
| Visit Information                        | Visit 0
Pre-Screening
Via
Phone or
Email
(optional) | Visit 1
Screening,
Baseline,
Randomization,
Treatment 1 Fit
& Dispense | Visit 2
Treatment 1
Follow-up,
Treatment 2
Fit &
Dispense | Visit 3
Treatment 2
Follow-up,
Final
Evaluation |
| Time Point                               | Pre-Visit  | Day 0   | Day 14 ± 2
after Visit 1  | Day 14 ± 2
after Visit 2                                 |
| Estimated Visit Duration                 | 15 min   | 2.0 hours   | 1.5 hours  | 1.5 hours   |
| Preliminary Subject Identification       | x  |   |  |   |
| Privacy Notice and Disclosure            | x  |   |  |   |
| CLDEQ-8 Questionnaire                    |  | x   | x  | x   |
| Statement of Informed Consent            |  | x   |  |   |
| Demographics                             |  | x   |  |   |
| Medical History/Concomitant Medications  |  | x   | x  | x   |
| Habitual Contact Lens Information        | x  | x   |  |   |
| Current contact lens wear times          |  | x   | x  | x   |
| Inclusion/Exclusion Criteria             |  | x   |  |   |
| Baseline Questionnaires                  |  | x   |  |   |
| Contact lens removal                     |  | x   | x  | x   |
| Entrance Snellen Visual Acuity           |  | x   | x  | x   |
| Keratometry                              |  | x   |  |   |
| Subjective Sphero-Cylindrical Refraction |  | x   |  | x   |
| Subjective Best Sphere Refraction        |  | x   |  |   |
| Slit Lamp Biomicroscopy                  |  | x   | x  | x   |
| Randomization                            |  | x   |  |   |
| Lens Selection                           |  | x   | x  |   |
| Lens Insertion                           |  | x   | x  |   |
| Lens Settling                            |  | x   | x  |   |
| Lens Fit Assessment                      |  | x   | x  | x   |

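### ARM 2 Visit 3 Step 3.6 names the Baseline CLUE and MRD form, although its own row label, Table 3 and both Steps 2.6 call for the Follow Up form

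*Combined protocol and SAP*

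**What the plan says.** The protocol distinguishes two versions of the CLUE and MRD questionnaire. Visit 1 Step 1.8, where subjects rate the habitual lens before randomization, uses the Baseline version. After two weeks of wear, Step 2.6 in ARM 1 (AO1D) and Step 2.6 in ARM 2 (habitual lens) both read: "The subject will respond to the CLUE and MRD Follow Up Questionnaire (Appendix A".

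The remaining administration is in the ARM 2 table headed "Visit 3: Treatment 2, 2-Week Follow-Up", after AO1D wear. The Procedure cell of Step 3.6 reads "Follow-up questionnaires", but the Details cell of the same row reads: "The subject will respond to the CLUE and MRD Baseline Questionnaire (Appendix A".

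In Table 3 for ARM 2, the row "Baseline Questionnaires" is marked at Visit 1 only. The follow-up questionnaire row is marked at Visits 2 and 3.

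Section 2.3 sets three secondary hypotheses. The first, change in CLDEQ-8, is between arms. For the others it says: "The remaining two secondary hypotheses will be evaluated within the second study arm only". They are CLDEQ-8 total score and CLUE comfort score at two weeks.

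Section 2.2 prints an MRD stem with two alternative referents: "Please think about your experience with your current contact lenses/ the study contact lenses". A second stem, on how often sensations occurred, has the same pair of alternatives.

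**The concern.** A site that follows the detailed procedure gives ARM 2 subjects one form after the habitual lens and another after AO1D. In that arm the form would then coincide exactly with the lens. The Section 14.6 model for within-ARM 2 CLUE comfort has lens type, baseline score and a random site effect, with no term that could separate form from lens. Any effect of the form on the answers would be read as a lens effect.

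If some sites follow Step 3.6 and others follow Table 3, the AO1D ratings come from mixed forms. The random site effect would not remove this, because it shifts a site's ratings of both lenses, whereas the form would change at Visit 3 only.

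The instruction is unlikely to be harmless background text. Section 15.1 says the eCRFs are designed to match the procedures at each visit, and Section 10 prohibits waivers. As written, following Step 3.6 departs from Table 3, and following Table 3 departs from Step 3.6. No later visit exists at which the ratings could be taken again.

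**Working it through.** There is no stated figure to reproduce. The check sets every CLUE and MRD administration beside the schedule.

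| Step | Lens just worn | Form named in Details | Form in Table 3 |
|---|---|---|---|
| 1.8, Visit 1, both arms | Habitual | Baseline | Baseline |
| 2.6, ARM 1 Visit 2 | AO1D | Follow Up | Follow-up |
| 2.6, ARM 2 Visit 2 | Habitual | Follow Up | Follow-up |
| 3.6, ARM 2 Visit 3 | AO1D | Baseline | Follow-up |

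Three of the four rows agree with Table 3. Step 3.6 does not, and it also disagrees with its own label. Of the three post-wear administrations, two name the Follow Up form.

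**What uses the Step 3.6 data.**
- The within-ARM 2 CLUE comfort hypothesis, margin -5 points (Sections 2.3 and 14.6). It contrasts AO1D at Visit 3 with the habitual lens at Visit 2.
- The within-ARM 2 item tests in Sections 2.3 and 14.7: 8 CLUE comfort + 8 CLUE vision + 8 MRD = 24 items.
- The subjects are those in ARM 2 who reach Visit 3, with about 40 targeted to complete.

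**What does not.**
- The primary comparison and the change in CLDEQ-8 take only the first period of ARM 2, so they use no Visit 3 data.
- The within-ARM 2 CLDEQ-8 total score comes from Step 3.5, which names no version.
- The preference items come from Step 3.7.

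**What is known about how the forms differ.**
- The stems offering current or study lenses introduce 2 + 3 = 5 of the 8 MRD items: P3_0006_p38 and p39, and P3_0023_p01 to p03. The other 3 MRD items carry no such stem.
- No section says which alternative belongs to which form.
- The CLUE comfort items listed in Section 2.2 refer to these lenses or name no lens.
- Appendix A is not shown, so the two forms cannot be compared.

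The conflict over which form to give is therefore established from the text. A change in the lens being rated is a possibility for five tertiary MRD items and unverified for CLUE.

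**The case against.** The strongest reply is that the intent is plain. One word conflicts with the row label, the visit heading, the schedule and two parallel steps, and it looks copied from Step 1.8. Experienced sites and the eCRF builder may well use the Follow Up form anyway.

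Even with the Baseline form in hand, the subject would probably rate AO1D. Subjects must arrive having worn the study lenses for at least two hours. Only study-provided lenses are allowed during the period. Step 3.6 comes before lens removal at Step 3.10, and wear time, compliance and symptoms have just been asked.

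Most of this stands. It shows which form was meant, and it makes a wrong-lens answer less likely. It does not tell a site which of two written instructions to follow, and it does not show that the two forms are equivalent.

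A reader might infer more: that ARM 2 subjects would rate the habitual lens twice, that the difference would be drawn to zero, and that the error would favour non-inferiority. The documents do not support this. The two-way stem is assigned to neither form and is not printed for CLUE comfort, the secondary endpoint. Nor is the direction fixed. The chosen sample size in Table 9 rests on a gain of 9 points, which lies 9 - (-5) = 14 points from the margin. A difference of zero lies 0 - (-5) = 5 points from it. Whether that helps or hinders a pass depends on AO1D's true effect and on the correlation between repeat ratings of one lens, which the documents do not give. This hypothesis is also tested only once the primary is met, and the primary uses no Visit 3 data.

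**Conclusion.** The point holds as an internal inconsistency that should be fixed. Step 3.6 is wrong as written, and it governs the only AO1D CLUE and MRD data in ARM 2. The exposure is one of three secondary hypotheses and 24 within-ARM 2 item tests, in about 40 subjects.

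That exposure is an upper limit. It assumes that sites or the eCRF follow the Details text. How far results would shift depends on differences between the forms that cannot be seen without Appendix A, so no numerical bias is claimed. If the CLUE sections of the two forms prove identical, only the label is wrong for the secondary endpoint. The study's main conclusion does not rest on this step.

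**What to change.** Change the Details text of Step 3.6 to name the CLUE and MRD Follow Up Questionnaire, in line with its row label, Table 3 and both Steps 2.6. Confirm that the Visit 3 eCRF carries that form, and check in Appendix A that its wording points to the lens worn in the second period. Do this before any ARM 2 subject reaches Visit 3. If some already have, record which form each was given.

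The cost is one phrase in the protocol, one eCRF check and the usual submission of a protocol revision to the IEC/IRB under Section 18.3. No subjects, visits or procedures are added.
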